## 6.6 Efficacy Assessments

The primary blinded read will be performed on all 450 human cases by a physician with more than 15 years of expertise in general breast imaging and with specific expertise in breast SHI ([name]). All imaging studies will be rated on a quasi-continuous scale from 0 to 100 ranging from “no lesion seen (no findings)” over “probably benign” and “indeterminate” to “malignant.” Using a quasi-continuous 100-point rating scale has an intuitive probabilistic interpretation and is known to improve the assessment of the characterization capabilities of the imaging modes studied [Wagner et al 2001].

The SHI images will be qualitatively analyzed as described above for the pulse inversion HI injection. The pre- and then post-contrast diagnostic US criteria (as detailed below) will be evaluated for each patient in two readings as follows: grayscale; grayscale and PDI (baseline); grayscale and contrast enhanced pulse inversion HI, and then in the second reading grayscale/baseline and SHI and, finally grayscale and SHI with dynamic CMI-SHI added. While this may introduce some bias from pre- to post-contrast results, we considered this the more realistic approach to how US contrast may be used in clinical practice. Moreover, such a “sequential” reading scheme may well produce the same total reader variance as a more independent reading scheme (where the evaluation of each imaging mode is separated in time by 1 month or more), while having the advantage of being logically much less demanding [Beiden et al 2002]. Each case will also be read by the two on-site investigators, blinded to the mammographic and histopathological diagnosis, to allow repeatability to be assessed for each site. Finally, each mammogram will be read by a radiologist as part of the patient’s standard clinical assessment and assessed using the BIRADS scale [ACR 1998].

Diagnostic US criteria (Evaluated for each imaging mode):

- Diagnosis; size, shape, and orientation of the lesion; echogenicity compared to surrounding tissue.

- Distribution of color signals and the overall color content of the lesion evaluated by comparing the pattern and amount of color to the normal surrounding breast.
  - If uniform, the color will be categorized as less intense, iso-intense or more intense than normal breast.
  - If non-uniform, the color will be described by location, intensity and distribution.

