- Irregularity of the course of the vessels will be scored on a scale from 1.0 to 5.0 (smooth to severe irregularity)
- Anastomoses between adjacent vessels will be noted (as 1-2, 3-5 or >5 vessels connecting).
- Enhancement pattern will also be graded as peripheral, radial from one or multiple sites, spotty or a combination.

Sensitivity, specificity, accuracy, positive predictive value (PPV) and negative predictive value (NPV) will be calculated for all six imaging modalities (the five different US modes and mammography). The dichotomous parameter needed for these calculations will be derived by ascertaining whether the radiologist would recommend a biopsy or not based on the imaging study in question. Inter- and intra-observer variability will also be calculated

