### 7.2 Statistical Analyses

#### 7.2.1 Hypotheses:

H1: SHI or pulse inversion HI will improve the diagnostic accuracy of mammography, grayscale US or power Doppler imaging to distinguish benign from malignant breast disease. The fundamental hypothesis is that the area under the ROC curve will improve by 0.10 to 0.15 with SHI compared to the other imaging modalities.

H2: Some findings of SHI (including perfusion estimates and CMI-SHI) or pulse inversion HI correlate with the pathological diagnosis of benign/malignant or with other significant physiological/pathological parameters. The fundamental hypothesis is that higher correlation coefficients can be achieved with SHI than with pulse inversion HI.

H3: 3D SHI estimates of perfusion correlate with absolute perfusion measured in the kidneys of dogs. The fundamental hypothesis is that correlation coefficients above 0.75 can be achieved for *in vivo* SHI perfusion estimates.

H4: *In vivo* fractional tumor vascularity measurements obtained with power Doppler imaging, pulse inversion HI or SHI correlate with iMVD or any other pathological measure of breast tumor vascularity obtained in the surgical biopsy specimens. The fundamental hypothesis is that higher correlation coefficients can be achieved with SHI than with the other two US flow modes.

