### 7.2.2 Analysis of Results

The findings of SHI, pulse inversion HI and PDI will be correlated to vascular morphology (i.e., tumor angiogenesis) and other pathological findings; including a) size b) vascularity, and c) type of mass. For cancers, pathological criteria, which will be evaluated, are the stage of the cancer, degree of proliferation and presence or absence of receptors. For the pre and post-contrast enhanced comparisons, dichotomous parameters (e.g., benign/malignant) and ranked data (less, iso, or more intense) will be analyzed with the McNemar test which measures significance of changes in related samples (pairwise comparisons). For variables in which accurate numerical measurement is possible (e.g., perfusion), the techniques will be compared using an ANOVA.

The ability of the imaging tests to distinguish benign from malignant masses will be compared using ROC analysis, while the incremental validity of imaging diagnosis and mammography will be analyzed using logistic regression and ROC analyses [DeLong et al. 1988; Metz 1986; Wagner et al. 2001]. The tests are: x-ray mammography, fundamental grayscale US imaging, PDI, pulse inversion HI and SHI (as well as SHI with CMI-SHI added), while pathology (based on excisional or core biopsies) will provide the reference standard. All studies will be rated on a quasi-continuous scale from 0 to 100, since this has an intuitive probabilistic interpretation and improves the assessment of the characterization capabilities of the imaging modalities compared to using a coarser 6-point scale [Wagner 2001]. Logistical regression techniques will be used to combine the 4 US imaging modes and mammography as well as to incorporate the quantitative parameters into the SHI diagnosis before repeating the ROC analysis. This will allow all possible combinations to be compared to one another (e.g., mammography versus all the US modes combined or mammography and grayscale US versus mammography and grayscale US and SHI, etc.). Differences between ROC curves will be tested by computing Mann-Whitney statistics.

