#### 7.2.4 Sample Size Calculation

A power analysis was performed using NCSS/PASS 2005 (NCSS, East Kaysville, UT) to estimate the number of cases required in the positive and the negative group (i.e., the malignant and benign cases, respectively) to achieve significance at the 0.05 level (on a two-sided test) when comparing binormal ROC curves (i.e., for specific aim 3) based on the primary reader ([name]) reading all cases.

For this study to demonstrate that 3D SHI produces a 10 % increase in diagnostic accuracy with 90 % statistical power requires between 400 and 600 patients (depending on the positive biopsy rate). If the real increase in accuracy is 15 %, then between 167 and 300 cases are needed to achieve 90 % power. Consequently, we selected a sample size of 450 patients for this clinical trial, which will allow us to detect a 15 % increase in the diagnostic accuracy of diagnosing breast cancer with over 90 % statistical power (assuming a positive biopsy rate of around 20 %). If the actual positive biopsy rate is approximately 30 %, then we will have more 90 % power to detect a 10 % increase in accuracy.

For Hypothesis # 3, we assumed that the correlation coefficient achievable with 3D SHI perfusion estimates will be 0.75 whereas our preliminary work with 2D SHI achieved a coefficient of 0.57 [Forsberg et al. 2006a]. This difference will be detectable with more than 80 % power at the 0.05 significance level (on a two-sided test) when 152 data points are analyzed. Hence, the decision to study 5 dogs for a total of 160 perfusion estimates. Finally, for Hypothesis # 4, we assumed that the correlation coefficient between power Doppler imaging and pathology will be approximately 0.40 (since our preliminary work [Caudhari et al. 2000; Forsberg et al. 2008] achieved coefficients between 0.25 and 0.49). Then we will have more than 80 % power to detect an improvement in the correlation by 0.3 or more due to SHI at the 0.05 significance level (using a two-sided test) when 84 patients are analyzed.

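### In the nested logistic comparisons the SHI term also carries a second reading of the grayscale images, so it can test positive too often when SHI adds nothing

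*Combined protocol and SAP*

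**What the plan says.** Section 6.6 has the primary reader rate every case from 0 to 100 in two readings. The first covers grayscale, grayscale with PDI, and grayscale with pulse inversion HI. The second continues: "and then in the second reading grayscale/baseline and SHI and, finally grayscale and SHI with dynamic CMI-SHI added". No baseline-only rating is listed for the second reading, and no rating of SHI without grayscale is listed anywhere. The section concedes that this order may introduce some bias from pre- to post-contrast results, and defends it as close to clinical use.

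Section 7.2.2 analyses incremental validity by logistic regression and ROC methods. It combines the mode ratings by logistic regression and gives as one example "mammography and grayscale US versus mammography and grayscale US and SHI". Differences between ROC curves are to be tested with Mann-Whitney statistics.

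The plan does not treat the reader as perfectly repeatable: "Inter- and intra-observer variability will also be calculated" (6.6, and again in 7.2.2). It gives no expected value. Section 7.2.1 sets the effect of interest: "the area under the ROC curve will improve by 0.10 to 0.15 with SHI".

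**The concern.** The base model holds one reading of the grayscale images. The larger model holds that reading plus a score that contains another reading of the same images, with its own reader error. Two imperfect readings of one image, combined, discriminate better than one. The larger model can therefore improve even if the SHI clips carry no diagnostic information.

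This differs from a reading-order effect: it would remain with counterbalanced sessions and a reader who remembered nothing. The caveat in 6.6 about pre- to post-contrast bias neither describes it nor corrects it.

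The primary objective (section 2) includes improvement in combination with other imaging modes. A significant SHI coefficient in these models could be reported as evidence of incremental value when part or all of it is the benefit of a second look at grayscale.

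**Working it through.** **The plan's own figure.** The documents state no error rate for the incremental test; they state sample sizes for the direct ROC comparison. Section 7.2.4 works "to achieve significance at the 0.05 level (on a two-sided test) when comparing binormal ROC curves". A 10% gain "produces a 10 % increase in diagnostic accuracy with 90 % statistical power requires between 400 and 600 patients"; for a 15% gain, "then between 167 and 300 cases are needed to achieve 90 % power"; and "we selected a sample size of 450 patients for this clinical trial". Baseline AUC and between-mode correlation are not given, so these cannot be reproduced from stated inputs alone. Assuming a baseline AUC of 0.60, correlation 0.35 and positive rates of 20-40%, a paired binormal calculation gives 605 and 403 patients for the 10% gain and 255 and 170 for the 15% gain. That matches three of the four stated bounds (not 300). With AUC 0.67 and correlation 0.3, 450 patients give 99.5% power (15% gain, 20% positive) and 91.5% (10% gain, 30% positive), in line with the plan. This point does not disturb those figures.

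**Inputs for the incremental test.**
- From the plan: N = 450; positive biopsy rate 20% or 30% (450 × 0.20 = 90 or 450 × 0.30 = 135 cancers); two-sided 0.05.
- Assumed: grayscale AUC 0.67 or 0.76. Section 1.1 reports pilot values of 0.64, 0.67 and 0.76 for the comparison techniques without assigning them to modes.
- Assumed: an independent mammography score with AUC 0.71.
- Assumed: within-class intra-reader ICC of 0.7 to 0.9.

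**Size of the artefact by formula.** Let the first rating be R1 = L + e1 and the second-session rating R2 = L + e2. L is the appearance of the case, e1 and e2 are independent reading errors, and SHI contributes nothing. With unit within-class variance for one rating, the mean of two has variance (1 + ICC)/2, so

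AUC(two readings) = Φ( Φ⁻¹(AUC) / √((1 + ICC)/2) ).

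For AUC 0.76, Φ⁻¹ = 0.706:
- ICC 0.9: 0.706/√0.95 = 0.725, AUC 0.766, gain 0.006
- ICC 0.8: 0.706/√0.90 = 0.744, AUC 0.772, gain 0.012
- ICC 0.7: 0.706/√0.85 = 0.766, AUC 0.778, gain 0.018

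These are for grayscale alone. With mammography in both models, and noise from the SHI clips in the joint rating, the gain is smaller, as the table shows.

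**Rejection rates by simulation.** SHI is uninformative, reading errors are independent, grayscale AUC is 0.76, mammography is in both models, and there are 800 runs per cell (error about 1-2 points). Paired entries are for 20% / 30% cancers.

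| ICC | Logistic test of SHI term (nominal 5%) | DeLong test on nested fits | Mean AUC gain | Logistic test, repaired base model |
|---|---|---|---|---|
| 0.9 | 28.6% / 34.1% | 1.3% / 1.8% | 0.0041 / 0.0037 | 6.0% / 5.5% |
| 0.8 | 61.3% / 69.3% | 6.0% / 9.4% | 0.0080 / 0.0077 | 5.4% / 4.8% |
| 0.7 | 82.0% / 89.1% | 15.4% / 21.5% | 0.0122 / 0.0119 | 6.6% / 4.6% |

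The repaired base model holds mammography, the first grayscale rating and a grayscale rating from the same second reading.

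**Sensitivity.**
- Lower AUC: at grayscale AUC 0.67 and 25% cancers, the logistic test rejects in about 18% of trials (ICC 0.9) and 54% (ICC 0.7).
- Carry-over of reading error: at error correlation 0.8 the logistic test rejects in about 6-19%. If the SHI clips add no noise to the rating, one cell (AUC 0.76, ICC 0.8, 30% cancers) gives 51%, 28% and 10% at error correlations 0.5, 0.8 and 0.95. If the first rating is carried forward unchanged, the rate is nominal (4-5%).
- Direct test of the joint rating against the grayscale rating, with two fresh readings: 4-6%.

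**The case against.** The strongest reply is that the high rates belong to a test of the logistic coefficient, whereas section 7.2.2 uses the regression to combine modes and names Mann-Whitney statistics for comparing the curves. That stands in large part. On nested fitted models the DeLong form of that test is very conservative: 0-0.4% under a true null with the repaired base model. With independent error it stays at about 1-3% at ICC 0.9 in the main setting. With error correlation 0.5 it is 0.8-5.3% at ICC 0.7 and no more than 2.0% at ICC 0.8-0.9. It is not safe at every repeatability, though: with independent error at AUC 0.76 it exceeds 5% from about ICC 0.8 downward. And 7.2.2 names logistic regression beside ROC analysis for incremental validity, so a coefficient test is within what the plan allows.

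A second reply is that independent reading error is the worst case. One reader working sequentially, with no stated washout, may carry the first impression forward. This also stands, and it is why the size is given as a range. The plan does not say that the first rating is carried forward, and it expects intra-observer variability.

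Three stronger readings are tempting, and the documents do not support them:
- That a positive combined result could never be told from the artefact. The spurious gain with mammography in the model is at most about 0.012, roughly an eighth of the smallest hypothesised gain (0.012/0.10 = 0.12).
- That the main result is compromised. Section 7.2.1 and the sample size rest on direct AUC comparisons between modes. Comparing the grayscale-plus-SHI rating with the grayscale rating is itself an in-combination comparison, and it is not inflated.
- That SHI is favoured over HI because HI is read in the same session as grayscale. This depends on a within-session error correlation that the documents do not give, and it was not calculated. No such claim is made.

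**Conclusion.** The point holds for the nested logistic comparisons and only there. As planned, the SHI term mixes any SHI information with a re-reading of the grayscale images, and its nominal 5% test can reject far too often when SHI adds nothing: roughly 18-34% at ICC 0.9 and 54-90% at ICC 0.7, for grayscale AUC 0.67-0.76, 450 patients, 20-30% cancers and independent reading error.

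These sizes depend on repeatability and error correlation, neither of which is in the documents. The direction does not: there is some inflation whenever the second reading has any fresh error. It is best treated as a correctable weakness in how incremental value is estimated, worth fixing before reading starts because the missing rating has to be collected at the time.

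**What to change.** In 6.6, have the existing primary reader record a 0-100 rating of the grayscale/baseline images at the start of the second reading, before the SHI clips are opened. In 7.2.2, put that rating together with the first-session grayscale rating in the base model of every comparison that adds SHI or CMI-SHI.

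The new rating must come from the same second reading. With it in the base model, the logistic test rejects in 3.5-6.6% of null trials. Adding a separate, independent grayscale re-reading instead still leaves 14-54%.

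If no rating can be added, base the reader-rated incremental claim on the direct paired AUC comparison of the grayscale-plus-SHI rating with the grayscale rating, and state in 7.2.2 that the SHI logistic coefficient is not to be read as incremental value. If the first rating is meant to be carried forward unchanged, 6.6 should say so.

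The cost is one extra rating per case on images already on screen, one or two sentences in 7.2.2, and a slightly smaller gain credited to SHI.

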A baseline US grayscale scan will be used to identify the mass or abnormal area seen by mammography (or another concomitant imaging mode, such as US or MRI) and to evaluate the following criteria: diagnosis; size, shape, and orientation of the lesion; echogenicity compared to surrounding tissue. Standard PDI of the lesion or target area will also be performed. The distribution of color signals and the overall color content of the lesion will be evaluated by comparing the pattern and amount of color to the normal surrounding breast. Irregularity of the course of the vessels and anastomoses will be evaluated. Digital clips of the two baseline imaging modes will be acquired (with videotaping as backup).

Patients will then receive a bolus, intravenous (IV) injection of 0.25 ml of Definity in a peripheral vein followed by 3D pulse inversion HI. The pulse inversion HI images will be analyzed similar to the baseline power Doppler images. Patients will then receive a second bolus, IV injection of up to 20  $\mu$ l/kg of Definity, followed by 3D SHI. The SHI images will be qualitatively analyzed as described above. All subjects will be closely monitored by a physician during and following the study (for 30 minutes as recommended by the FDA).

The entire examination will be recorded as digital loops, as well as on VHS videotape. Baseline and contrast-enhanced US imaging findings will be recorded.

In addition, all subjects will be scheduled to undergo a clinically indicated breast biopsy core / excisional / lumpectomy of the mass or region of abnormality or mastectomy within 30 days after the US study procedure. Apart from diagnosis, the pathologist will provide the following when possible: estrogen progesterone and HER2 receptor presence or absences; presence or absence of hemorrhagic, necrotic, or other component of the lesion (and their location if present); histological margins; lesion size; TNM staging; histological lesion type; presence or absence of vascular invasion; histological and cytological grade; presence or absence of metastases; node staging; and percentage of the lesion that was invasive or *in situ*.

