## INTRODUCTION

### Background

X-ray mammography is efficacious in the detection and differentiation of a high percentage of breast masses. However, in a significant number of patients mammography cannot differentiate between benign and malignant circumscribed masses [Feig 1992]. Solid breast masses are best managed by biopsy or close follow-up [Jackson 1990]. Thus, the development of a technique, which can reliably differentiate benign from malignant solid masses, should result in earlier cancer detection and reduce unnecessary biopsies as well as eliminate patient anxiety from follow-up.

While US imaging complements x-ray mammography in the pre-operative diagnosis of palpable breast tumors, its main use is restricted to differentiating between cystic and solid masses [Burns et al 1982]. To improve the usefulness of US and to aid in the differentiation of benign from malignant lesions both color and pulsed Doppler have been utilized. Pulsed Doppler investigations have found differences in the neovascularity of benign and malignant tumors [Burns et al 1982; Madjar 1991; Bohm-Velez & Mendelson 1989]. However, overlap between the two groups has been reported [Bohm-Velez & Mendelson 1989; Adler et al 1990], indicating that more sensitive techniques, such as color Doppler imaging (CDI) [Adler et al 1990; Madjar 1992; Cosgrove et al 1990; Hamada et al 1992; Cosgrove et al 1993], need to be employed. The results of applying CDI to breast cancer diagnosis are mixed ranging from very positive [Hamada 1992] to quite negative [Adler et al 1992].

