## 4. TRIAL POPULATION

This trial will consist of up to 450 adult (18 years of age or older) female subjects who are scheduled for excisional biopsy for a breast mass or abnormality identified on mammography.

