#### 4.1 Inclusion Criteria

All subjects accepted for this trial must:

- Be a female diagnosed by x-ray mammography (performed within 90 days prior to the study procedure) as having a solid breast mass or abnormal area without a mass.
- Be scheduled for a biopsy (core / excisional / lumpectomy) of the mass or region of abnormality or for mastectomy within 30 days after this study procedure.
- Be at least 18 years of age.
- Be medically stable.
- If a female of child-bearing potential, must have a negative pregnancy test.
- Have signed Informed Consent to participate in the study.

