#### 6.3 Ultrasound Imaging

The US examinations will be performed by a qualified sonographer. Procedures and equipment for this trial will be used in accordance with typical clinical procedures. In particular, the mechanical index will be set to less than 0.8 on the US scanner. All trial procedures will be conducted in accordance with Good

Clinical Practice. For the ultrasound examination, the patient will be asked to lie in the supine position and a catheter will be placed in a superficial vein (preferably an antecubital vein). Acoustic coupling gel will be applied to the breast area of interest. A baseline US grayscale scan will be used to identify the mass or abnormal area seen by mammography (or another concomitant imaging mode such as US or MRI). Standard PDI of the lesion or target area will also be performed.

Following baseline imaging, patients will receive a bolus, IV injection of 0.25 ml of Definity and the mass or area of abnormality will be imaged with the broad bandwidth linear array (selected in the development phase described above) and a 30 to 40 second digital clip of the 3D pulse inversion HI volume data, covering baseline to beyond peak enhancement, will be acquired. The point of maximum enhancement in the pulse inversion harmonic images will be assessed visually (by the on-site investigators in consensus) and at least 10 seconds of data will be acquired past this time point. Subsequently more sweeps of the abnormality will be stored on the scanner hard drive every 1 to 2 minutes through the period of enhancement (up to 5 minutes).

After a 30 minutes waiting period patients will receive a second bolus, IV injection of up to 20  $\mu$ l/kg of Definity, sweeps of the mass or abnormal area will be made to acquire 3D SHI grayscale volume data through the period of enhancement (up to 2 minutes in our pilot study). It should be noted, that all subjects will be closely monitored by a physician during and following the study (for 30 minutes as recommended by the FDA) [FDA Alert 2007/2008]. Additionally, resuscitation equipment and trained personnel will be in immediate proximity to the patient during the study.

All images (baseline and contrast-enhanced) will be obtained using a broad bandwidth, 3D, linear array, and will include images of the entire area of interest. The entire examination will be recorded as digital loops, as well as on VHS videotape.

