All histopathological variables will be compared to imaging judgments on diagnoses and characteristics of vascularity for the different modalities. When both sets of variables are nominal, chi-square tests will be conducted. When both types of variables are ordinal or continuous, correlations will be calculated. When one type of variable is nominal and one continuous non-parametric rank order tests such as Mann-Whitney U-tests or Kruskal-Wallis tests will be performed [Rosner 1990]. Inter- and intra-observer variability will also be determined by calculating the intraclass correlation coefficient and the kappa statistic [Shrout 1979; McGraw 1996].

Comparisons of sensitivities, specificities and accuracies for diagnosing cancer with the different imaging modalities will be conducted with McNemar's test for correlated proportions (against the histopathological gold standard). All of the statistical analyses proposed for the human clinical trial will be repeated split by racial and ethnic groups to determine if clinically important race/ethnicity differences exist in the ability of 3D SHI to diagnose breast cancer.

Finally, the vascularity measures obtained from the subgroup of up to 85 CD31 stained breast tumor specimens will be compared to the fractional tumor neovascularity data to determine if any correlation exists (in baseline PDI or one of the two contrast enhanced modes). The existence of a linear relationship between ultrasonic and pathologic data will be assessed using single variable linear regression techniques and reverse stepwise multiple linear regression analysis.

All analyses and computations will be performed using NCSS/PASS 2005 and Stata 9.0 (Stata Corporation, College Station, TX), while the study database will be designed and implemented in Filemaker Pro 10.0 (Filemaker Inc, Santa Clara, CA). This database will contain all patient information (except names and other identifiers), including the answers to the questionnaire, and the results of the various US imaging modes as well as the pathology results.

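### Entry on a mammographic abnormality plus a scheduled biopsy largely fixes mammography's biopsy-recommendation result, so the McNemar tests of specificity, and usually accuracy, tilt towards ultrasound

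*Combined protocol and SAP*

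**What the plan says.** - **Entry.** Section 4.1 requires each subject to "Be a female diagnosed by x-ray mammography" with a mass or abnormal area, and to "Be scheduled for a biopsy (core / excisional / lumpectomy) of the mass or region of abnormality" or for mastectomy. Section 4 describes the population as "scheduled for excisional biopsy for a breast mass or abnormality identified on mammography".
- **Binary result.** Section 6.6 lists six modalities, mammography among them. The positive/negative call for each is "derived by ascertaining whether the radiologist would recommend a biopsy or not based on the imaging study in question".
- **Test.** Section 7.2.2 plans McNemar's test, against pathology, for "Comparisons of sensitivities, specificities and accuracies for diagnosing cancer with the different imaging modalities".
- **Other routes to the lesion.** The Synopsis says that the target may have been seen on mammography "or another concomitant imaging mode, such as US or MRI"; section 6.3 repeats this. The share of such women is not given.
- **Which mammogram read.** Section 6.6 describes the routine clinical read, scored by BIRADS. Section 7.2.3 has the blinded reviewers fill in a worksheet for mammography.
- **Selection on ultrasound.** Section 4.2 excludes lesions that unenhanced ultrasound shows to be clearly cystic.

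No section mentions that entry depends on one of the tests compared, corrects for it, or limits the McNemar tests to the ultrasound modes. The only reading bias named, in section 6.6, is the one from sequential reading.

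**The concern.** Mammography is a comparator, but it is also the gateway to the trial. A woman whose mammogram would not have led to biopsy has little chance of entering, so mammography's true negatives and its missed cancers are both under-represented. The ultrasound modes face no filter of similar strength. Observed mammographic specificity falls because of who was enrolled, and accuracy usually falls with it.

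A significant gain in specificity or accuracy over mammography could therefore arise from the entry criteria and not from subharmonic or harmonic imaging. The primary objective names mammography as a comparator, so such a p-value would probably be quoted.

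**Working it through.** **Assumption that sets the size.** The mammogram read analysed is the one that drove referral (the clinical BIRADS read of 6.6). The third row of the table relaxes this.

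**The plan's own figures.** There are none for the McNemar tests. N = 450 is for comparing ROC areas and is not disputed here. Section 7.2.4 supplies the positive biopsy rates: 20% (90 malignant, 360 benign) and 30% (135 and 315).

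**Limiting case: every enrolled mammogram is positive.** Sensitivity is 100%, specificity 0%, and accuracy equals the positive biopsy rate p. All discordant benign pairs then favour ultrasound.
- Six ultrasound no-biopsy calls among benign lesions give exact p = 2 × 0.5^6 = 0.031; five give 2 × 0.5^5 = 0.0625. Six calls are a specificity of 6/360 = 1.7% or 6/315 = 1.9%.
- Ultrasound wins on accuracy when its specificity exceeds [p/(1 − p)] × (1 − sensitivity). At 90% sensitivity this is 0.25 × 0.10 = 2.5% (p = 20%) or 0.429 × 0.10 = 4.3% (p = 30%).

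**Two tests equal before referral.** The documents give no sensitivities or specificities, so these inputs are assumed: binormal equal-variance scores, ROC area 0.80, specificity 70%, correlation 0.3 given true status. The separation is √2 × 0.842 = 1.190 and the threshold 0.524, so sensitivity is Φ(1.190 − 0.524) = 0.747. The bivariate normal probability that both tests are positive is 0.591 in malignant and 0.128 in benign cases.

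- Only mammogram-positive women referred: ultrasound specificity = 1 − 0.128/0.300 = 0.573; sensitivity = 0.591/0.747 = 0.791.
- Mammogram re-read correlated 0.8 with the referral read (joint probabilities 0.666 and 0.211): mammography specificity = 1 − 0.211/0.300 = 0.296; sensitivity = 0.666/0.747 = 0.891.
- Half of the mammogram-negative, ultrasound-positive women also referred. Benign: 0.300 + 0.5 × (0.300 − 0.128) = 0.386, so specificity is 0.086/0.386 = 0.223 v 0.172/0.386 = 0.445. Malignant: 0.747 + 0.5 × (0.747 − 0.591) = 0.825, so sensitivity is 0.747/0.825 = 0.906 v 0.669/0.825 = 0.811.
- All of them referred: both tests are selected alike and the gap is nil.

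Each cell is mammography v ultrasound. Accuracy is 0.2 × sensitivity + 0.8 × specificity, before rounding. ROC areas come from simulation with 1.5 million cases per class.

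| Referral and read | Specificity | Sensitivity | Accuracy | ROC area |
|---|---|---|---|---|
| Before referral | 70% v 70% | 75% v 75% | 71% v 71% | 0.80 v 0.80 |
| Same read, mammogram-positive only | 0% v 57% | 100% v 79% | 20% v 62% | 0.69 v 0.76 |
| Re-read, correlation 0.8 | 30% v 57% | 89% v 79% | 42% v 62% | not computed |
| Same read, plus half of ultrasound-positives | 22% v 45% | 91% v 81% | 36% v 52% | 0.70 v 0.73 |
| Same read, plus all ultrasound-positives | 36% v 36% | 83% v 83% | 46% v 46% | 0.71 v 0.71 |

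**How firm is the sensitivity direction?** Simulated trials of 450 with exact McNemar tests used two equal tests (assumed sensitivity 85%, specificity 55% or 85%, correlation 0 or 0.5). Mammography is favoured on sensitivity in 94–100% of trials when no enrolled mammogram is negative, in 37–75% when 5% are, and in 8–18% when 10% are. At 20%, ultrasound is favoured in 7–17%. The direction turns once the share of enrolled cancers with a negative mammogram exceeds mammography's true miss rate.

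**Why only usually for accuracy?** Take an ultrasound read that is a coin flip, and let 5% of enrolled cancers be mammogram-negative. Mammography matches its 50% accuracy when it is negative in (0.5 − 0.2 × 0.95)/0.8 = 39% of benign cases (p = 20%) or (0.5 − 0.3 × 0.95)/0.7 = 31% (p = 30%). Above that, the accuracy contrast runs the other way.

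**The case against.** **This is the intended-use population.** The Background aims to "reduce unnecessary biopsies as well as eliminate patient anxiety from follow-up", and among women already referred low mammographic specificity is the clinical problem. A paired test there is a valid test of a conditional contrast. That stands, and it is why conclusions should be limited to referred women. It does not rescue a superiority test against a comparator whose result entry has nearly fixed; benign biopsies averted against cancers missed answers that aim directly.

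**The size is uncertain.** This stands in full. It depends on which mammogram read is analysed, on which 6.6 and 7.2.3 differ, and on how mammogram-negative women enter. A re-read shrinks the bias but keeps its direction as long as it tracks the referral read more closely than ultrasound does.

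**Ultrasound is selected too.** The cyst exclusion in 4.2 lowers the specificity advantage somewhat, mainly for grayscale.

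**Stronger readings a reader might infer.** One is that mammography must score exactly 100% and 0%. The documents do not support this: the target may be seen on ultrasound or MRI, and 4.1 does not say that the mammogram alone prompted the biopsy. Another is that sensitivity always favours mammography; the simulation shows that this can vanish or reverse. A third is that the primary comparison and sample size fail. Sections 7.2.1 and 7.2.4 rest these on ROC area, and 6.6 reports sensitivity and predictive values beside specificity, so the trade-off stays visible.

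**Conclusion.** The concern holds for the McNemar comparisons with mammography. As planned, they give specificity, and usually accuracy, p-values that enrolment largely creates. Under the assumptions shown, two equal tests differ in specificity by 57 percentage points when the referral read is analysed and only mammogram-positive women enter. The gap is 27 points with the re-read and about 22 with half of the ultrasound-positive women added. It is nil if all of them are added, although the mammographic entry criterion in 4.1 makes so open a route unlikely. The sensitivity tilt towards mammography is conditional on few enrolled cancers being mammogram-negative.

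The quantified first hypothesis and N = 450 are not decided by this dichotomy. The mammography ROC area is nevertheless lowered by the restricted range of ratings. In the main case the spurious gap is about 0.07, against a hypothesised gain of 0.10 to 0.15, so the ROC contrast needs the same limit on interpretation. The point should be fixed; it does not undermine the design.

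**What to change.** In sections 6.6 and 7.2.2:

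1. Make no superiority claim over mammography from McNemar tests on the biopsy-recommendation dichotomy. Report mammography's results on it descriptively, with sensitivity and specificity together, as benign biopsies potentially averted against cancers missed. Keep McNemar inference for comparisons among the ultrasound modes, noting that the cyst exclusion in 4.2 selects on grayscale.
2. Limit all conclusions against mammography, including ROC area and incremental value, to women with a mammographic abnormality already referred for biopsy.
3. State which mammogram read enters the analysis and reconcile 6.6 with 7.2.3, because this sets the size of the bias. The answer must respect the blinding of the on-site readers to the mammographic diagnosis in 6.6.

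Items 1 and 2 are wording. Item 3 may need a named mammogram reader or a set reading order. No extra patients or imaging are needed. The price is that the sponsor gives up a favourable-looking significance test against mammography. The differing rating scales (0–100, BIRADS, 1–5) are a separate matter.
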